**Table 3: Analysis Method and Analysis Set for Special Focus Efficacy Endpoints**

Efficacy Parameter	24-Week Analysis (Study Period: Dose Titration Period)	Final Analysis (Study Period: Entire Study)	Analysis Method	Analysis Set
Hgb	Change from Baseline to Week 24*	Change from Baseline to Week 48	MMRM	PP 
Hgb	Change from Baseline at Week 24	Change from Baseline at Week 48	ANCOVA	PP  Completers
Hgb	Time from Randomization to First Increase from Baseline Hgb >= 0.5 g/dL	Not Applicable	Kaplan-Meier	PP 
TSAT, ferritin, phosphate, bicarbonate, eGFR	Change from Baseline to Week 24	Change from Baseline to Week 48	MMRM	PP 
PTH, c-terminal and intact FGF-23	Change from Baseline to Week 24	Change from Baseline to Week 48	ANCOVA	PP 
FACIT score	Change from baseline at Week 24	Change from Baseline to Week 48	Descriptive	PP 
WPAI	Change from Baseline to Week 24	Change from Baseline to Week 48	Descriptive	PP 
Hospitalizations	Number and Duration ( days)	Number and Duration ( days)	Descriptive	PP 

Hgb, TSAT, ferritin, phosphate	Change from Baseline to Week 24	Change from Baseline to Week 48  Change from Baseline to Week 24	MMRM	FAS subjects who received permitted ESA Rescue Therapy
Hgb, TSAT, ferritin, phosphate		Change from Baseline to Week 48  Change from Baseline to Week 24	MMRM	PP Dosing sequence groups

\* Hgb change from baseline to Week 24 is the primary endpoint.

The analysis set used will either be the modified PP Analysis Set (24-Week Analysis snapshot) or PP Analysis Set (24-Week and Final Analysis).

## 8.2. Primary Efficacy Analysis

The primary efficacy endpoint is change from Baseline Hgb value at Week 24. A two-sided 95% confidence interval will be constructed for the mean change from Baseline in Hgb at Week 24 for each of the starting dose treatment groups, for subjects in the PP/mPP analysis set.

Results obtained using the Mixed Model Repeated Measures (MMRM) model will be used to construct the confidence intervals. The SAS procedure PROC MIXED with method specified as residual maximum likelihood (REML) will be used to fit the model and obtain the least squares mean, the associated standard error and two-sided 95% confidence interval for each treatment.

Under an assumption that the missing observations are missing at random, change from baseline Hgb at Week 24 will be analyzed by using a MMRM model with an intercept term, baseline Hgb as a covariate, starting dose treatment group effect, visit, visit by starting dose treatment group interaction, baseline Hgb by visit interaction and a random error term.

For the MMRM model, the Kenward-Roger method for approximating the denominator degrees of freedom and correcting for bias in the estimated variance-covariance of the fixed effects will be used. This will be achieved by specifying the DDFM = KR option in the MODEL statement within PROC MIXED. An unstructured variance-covariance matrix will be used to model the within-subject covariance. If the unstructured covariance configuration results in a lack of convergence, then the following variance-covariance matrix will be used, in the order listed below, stopping with the first that converges:

- Heterogeneous Toeplitz
- Heterogeneous first-order autoregressive
- Heterogeneous compound symmetry

---

Document: \\quintiles.net\enterprise\apps\sasdata\sasb\sas\Keryx\KRX-0502\Biostatistics\Documentation\SAP\

- Toeplitz
- First Order Autoregressive
- Compound symmetry

If all variance-covariance matrices selected fail to converge, variance components will be used as the next attempt at convergence.

To check the model assumption regarding normality for residuals and to detect potential outliers a normal probability plot of residuals and a plot of the residuals versus the fitted values will be used. If necessary, transformations and/or dropping of outliers to obtain data that meet the model assumptions will be implemented.

A table displaying, by visit and starting dose, the descriptive statistics for Hgb and the change from Baseline Hgb, the least squares mean (LSM) change from Baseline Hgb obtained using the MMRM described above and the corresponding 95% confidence interval of the mean change from baseline Hgb for each starting dose treatment group and these two groups combined will be presented for the 24-Week Analysis.

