15.2. Determination of Sample Size

Because this is an open-label Phase 4 study designed to estimate within-group changes from Baseline and describe time trends of iron parameters in sub-groups of subjects, it is appropriate to conduct a precision-based sample size estimation as opposed to a power-based calculation. The primary endpoint of interest is change in Hgb from Baseline at Week 24. The SD for that endpoint is estimated as 0.9 g/dL based on the Week 16 data in a prior Phase 3 study in a similar population (Study 306).

Assuming a population SD of 0.9 g/dL, with a sample size of 140 subjects, the 95% confidence intervals (CIs) for mean change in Hgb from Baseline to Week 24 can be estimated, allowing for a CI half-width of 0.149 g/dL.

It is assumed that 30% of the subjects in this study will drop out or be otherwise excluded from the PP population. Hence, 200 subjects will be randomized to ensure that there will be sufficient subjects at the end of the study for the longitudinal analyses (ie, 70 evaluable subjects in each randomized treatment group). Based on prior clinical trial experience, it is estimated that half of the subjects will stay on their starting dose, and the other half will increase their dose after 12 weeks of treatment. Hence, it is expected that the 4 dosing sequence groups that will arise will have approximately equal numbers of subjects (ie, 35 subjects are expected in each of the four dosing sequence groups (3-3, 3-6, 4-4, and 4-6 tablets/day).

The proposed sample size and the sizes of the sub-groups of interest are deemed sufficient for the analyses proposed below including the longitudinal analyses.

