15.7.1. Primary Efficacy Endpoint Analyses

The change in Hgb from Baseline is the primary endpoint of interest. Ninety-five percent CIs will be constructed for change from Baseline at Week 24 and change from Baseline at Week 48 based on the entire sample and by randomized dose groups. No imputation will be performed for these analyses.

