15.10. Other Statistical Issues

15.10.1. Significance Levels

Unless otherwise specified, all tests will be 2 tailed using a 0.05 level of significance. All CIs will be 2-sided 95% CIs.

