### 4.3. Sample Size Considerations

#### 4.3.1. Sample Size Justifications

Because this is an open-label Phase 4 study designed to estimate within-group changes from Baseline and describe time trends of iron parameters in subgroups of subjects, it is appropriate to conduct a precision-based sample size estimation as opposed to a power-based calculation. The primary endpoint of interest is change in Hgb from Baseline at Week 24. The standard deviation

(SD) for that endpoint is estimated as 0.9 g/dL based on the Week 16 data in a prior Phase 3 study in a similar population (Keryx Study KRX-0502-306).

Assuming a population SD of 0.9 g/dL, with a sample size of 140 subjects, the 95% confidence intervals (CIs) for mean change in Hgb from Baseline to Week 24 can be estimated, allowing for a CI half-width of 0.149 g/dL.

It is assumed that 30% of the subjects in this study will drop out or be otherwise excluded from the PP population. Hence, 200 subjects will be randomized to ensure that there will be sufficient subjects at the end of the study for the longitudinal analyses (i.e., 70 evaluable subjects in each randomized treatment group). Based on prior clinical trial experience, it is estimated that half of the subjects will stay on their starting dose, and the other half will increase their dose after 12 weeks of treatment. Hence, it is expected that the 4 dosing sequence groups that will arise will have approximately equal numbers of subjects (i.e., 35 subjects are expected in each of the four dosing sequence groups (3-3, 3-6, 4-4, and 4-6 tablets/day).

The proposed sample size and the sizes of the subgroups of interest are deemed sufficient for the analyses proposed below including the longitudinal analyses.

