### **8.3. Secondary Efficacy Analyses**

For the Final Analysis, the secondary efficacy endpoint, change from Baseline Hgb at Week 48 will be assessed in the same manner, using data for all visits up to and including the Week 48 visit, as described in section 8.2 for the Week 24 visit.

The 95% CI for the mean change from baseline will be obtained for each of the following secondary efficacy endpoints by using an MMRM:

1. Change in transferrin saturation (TSAT) from Baseline at Weeks 24 and 48
2. Change in ferritin from Baseline at Weeks 24 and 48
3. Change in serum phosphate from Baseline at Weeks 24 and 48
4. Change in eGFR from Baseline to Weeks 24 and 48
5. Change in bicarbonate from Baseline to Weeks 24 and 48

The same type statistics as described in Section 8.2 for Hgb will also be provided for the endpoints listed above where the change from Baseline to Week 24 results and the change from Baseline to Week 48 results will be presented in tables for the 24-Week analysis and the Final analysis, respectively.

Ninety-five percent CIs will be constructed for mean change from Baseline Hgb at Week 24 and mean change from Baseline Hgb at Week 48 based on the data for the PP analysis subjects who complete their Week 24 visit and data for the PP analysis subjects who complete their Week 48

visit, respectively, by starting dose treatment group and these two groups combined. The parametric analysis of covariance (ANCOVA) model for change from baseline in Hgb at Week 24 and at Week 48 with an intercept term, baseline Hgb as a covariate, starting dose treatment group effect, and a random error will be used to obtain the least squares mean (LSM), the associated standard error and associated 95% confidence intervals. To check the model assumption regarding normality for residuals and to detect potential outliers a normal probability plot of residuals and a plot of the residuals versus the fitted values will be used. If necessary, transformations and/or dropping of outliers to obtain data that meet these assumptions will be implemented.

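### The LS-mean confidence intervals for within-group and combined mean change treat the sample's mean baseline Hgb as known, so they are somewhat too narrow unless the baseline slope is zero

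*SAP*

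**What the plan says.** **Sizing.** Protocol 15.2 and SAP 4.3.1 size the trial on precision for a mean change, not on power for a comparison. The protocol's premise is "Assuming a population SD of 0.9 g/dL, with a sample size of 140 subjects", and the result is given as "allowing for a CI half-width of 0.149 g/dL". The SD is that of the change itself, without baseline adjustment: "The SD for that endpoint is estimated as 0.9 g/dL based on the Week 16 data in a prior Phase 3 study".

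**Protocol analysis.** Section 15.7.1 reads: "Ninety-five percent CIs will be constructed for change from Baseline at Week 24 and change from Baseline at Week 48 based on the entire sample". It adds intervals by randomized group and rules out imputation. The MMRM is described separately, under the secondary analyses in 15.7.2.

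**SAP analysis.** Section 8.2 changes the source of the primary interval: "Results obtained using the Mixed Model Repeated Measures (MMRM) model will be used to construct the confidence intervals". The model contains baseline Hgb, starting-dose group, visit, group-by-visit and baseline-by-visit, with an unstructured covariance and the Kenward-Roger method. The end of 8.2 presents the resulting interval as one for mean change in Hgb, for each starting-dose group and for both combined.

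Section 8.3 applies the same approach to TSAT, ferritin, phosphate, eGFR and bicarbonate. For Hgb in subjects who complete the visit it uses an ANCOVA with an intercept, "baseline Hgb as a covariate, starting dose treatment group effect, and a random error will be used to obtain the least squares mean (LSM"), and it carries that ANCOVA over to iPTH and both forms of FGF23.

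**What is not stated.** Neither section gives the baseline value at which LS means are evaluated, and neither adds a term for sampling variation in mean baseline. SAP 9.6 declares the added baseline-by-visit term. It does not declare that the primary interval has moved from the Protocol 15.7.1 method to the MMRM LS mean.

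**The concern.** A baseline covariate does no harm to the standard error of a difference between randomized groups, because the mean baseline at which both LS means are evaluated cancels. This trial's primary result is not a difference. It is a mean change within each group and over both groups. For a single mean, the LS-mean standard error carries only the residual variance left after regression on baseline, and takes the average baseline as a constant. Another sample of subjects would have another average baseline, and the mean change would move with it by the slope.

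Because the trial was sized on precision, the width of this interval is its main inferential output. An interval that leaves out one source of variation can look tighter than the planning figure without more information having been collected, and it can cover the population mean change less often than its label says. Change is calculated by subtracting the same baseline value (SAP 6.5.3), so a negative slope is to be expected, though its size is not known.

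**Working it through.** **Inputs from the documents**
- SD of change 0.9 g/dL and 140 evaluable subjects combined (Protocol 15.2).
- "70 evaluable subjects in each randomized treatment group" (Protocol 15.2).
- "All CIs will be 2-sided 95% CIs" (Protocol 15.10.1), so z = 1.96.

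**Input that is assumed**
- ρ, the correlation between baseline Hgb and change at Week 24. The documents do not give it; |ρ| from 0 to 0.6 is examined.

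**Step 1: reproduce the plan's figure.** 1.96 × 0.9 / √140 = 0.149 g/dL, as stated. Sample size: 140 / 0.70 = 200, also as stated. The planned precision therefore rests on the full SD of change for both groups combined.

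**Step 2: variance used by the LS-mean interval.** With complete data, an unstructured covariance and baseline-by-visit terms, the Week 24 MMRM LS mean equals the Week 24 ANCOVA LS mean. Its model-based variance is
- combined: 0.9² × (1 − ρ²) / 140
- per group: about 0.9² × (1 − ρ²) / 70

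**Step 3: variance over repeated samples of subjects.** The omitted term is slope² × Var(baseline) / N. Since slope = ρ × 0.9 / SD(baseline), it equals ρ² × 0.9² / 140, whatever the baseline SD. Adding it gives
- combined: 0.9² / 140, which is the planning variance
- per group: 0.9² × (1 − ρ²) / 70 + ρ² × 0.9² / 140 = 0.9² × (1 − ρ²/2) / 70

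Kenward-Roger does not restore the term. It corrects the covariance of the fixed effects, and mean baseline is not one of them.

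**Step 4: coverage.** Coverage is 2Φ(1.96 × ratio) − 1, where ratio is the model-based SE divided by the SE from Step 3: √(1 − ρ²) combined, and √[(1 − ρ²)/(1 − ρ²/2)] per group.

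| Assumed \|ρ\| | Combined half-width (0.149 needed) | Combined coverage | Per-group half-width: model / needed | Per-group coverage |
|---|---|---|---|---|
| 0 | 0.149 | 95.0% | 0.211 / 0.211 | 95.0% |
| 0.2 | 0.146 | 94.5% | 0.207 / 0.209 | 94.8% |
| 0.3 | 0.142 | 93.9% | 0.201 / 0.206 | 94.4% |
| 0.4 | 0.137 | 92.8% | 0.193 / 0.202 | 93.9% |
| 0.5 | 0.129 | 91.0% | 0.183 / 0.197 | 93.0% |
| 0.6 | 0.119 | 88.3% | 0.169 / 0.191 | 91.7% |

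**Step 5: simulation.** In 20,000 simulated two-group ANCOVA data sets per value (70 per group, complete data), combined coverage was 94.7%, 94.0% and 91.2% at |ρ| = 0.2, 0.3 and 0.5. Per-group coverage was 94.7%, 94.3% and 93.4%. The unadjusted combined interval covered 94.9% to 95.2%. In a second simulation of the same design, adding the omitted term gave 94.7% to 95.1%.

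**Step 6: which ρ is plausible?** For scale only, take a baseline SD of 0.5 to 0.87 g/dL; the upper value is a uniform spread over the 8.5 to 11.5 g/dL entry window, 3/√12. With slopes of −0.2 to −0.6, |ρ| runs from 0.2 × 0.5 / 0.9 = 0.11 to 0.6 × 0.87 / 0.9 = 0.58.

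**The case against.** The strongest reply is that the interval is valid conditional on the observed mean baseline. SAP 8.2 frames the estimate in terms of the subjects in the analysis set, and no section asks for coverage over re-sampled baselines. The baseline mix also depends partly on an entry window that Amendment 1 widened, so a fixed population mean baseline is not self-evident. The conditional validity stands. It does not settle the matter, because both documents give the aim as estimating within-group changes and base the 0.149 half-width on the unconditional SD of change. Nothing in the SAP says the target was narrowed to a mean at a fixed baseline.

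Several other points stand and limit the size.
- ρ is unknown, and at |ρ| of 0.2 to 0.3 the combined half-width loses only 0.003 to 0.007 g/dL.
- The per-group intervals, which 8.2 names first, are affected less than the combined one.
- Uncertainty in the borrowed SD matters about as much: at SD 1.0 the half-width would be 1.96 × 1.0 / √140 = 0.166, a shift of 0.017.
- The SAP tabulates descriptive statistics for the change, so a reader could derive an unadjusted interval.
- The calculations assume complete data at one visit, whereas the plan is an MMRM with 30% loss or exclusion. Missing values alter the exact figures but do not supply the omitted term.

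A reader might infer that the unadjusted interval of Protocol 15.7.1 should simply replace the MMRM. The documents do not support that. Subjects leave the study after IV iron or transfusion (Protocol 9.2.1), or after two low Hgb values when the rescue conditions are not met (9.2.2). Under dropout related to Hgb, a mean of the observed changes can be off-centre, and its good coverage with complete data says nothing about that.

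**Conclusion.** The point holds as a modest defect of precision. As written, SAP 8.2 and 8.3 give intervals for mean change that omit one variance component, so they are somewhat too narrow for the population mean change whenever the baseline slope is not zero. For |ρ| of 0.2 to 0.5, combined coverage is about 94.5% down to 91.0% and per-group coverage about 94.8% down to 93.0%. Per-group intervals stay at roughly 94% to 95% for |ρ| up to 0.4.

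This rests on three assumptions: the value of ρ, evaluation of LS means at the sample mean baseline, and complete Week 24 data.

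Three stronger readings are tempting and not supported:
- **That coverage is known to fall well short, for example to about 88%.** That needs |ρ| = 0.6. With an assumed baseline SD of 0.7 g/dL the slope would be 0.6 × 0.9 / 0.7 = 0.77 in size, so a 1 g/dL baseline difference would shrink to about 0.23 by Week 24. Nothing in the documents points to this.
- **That the iron, phosphate or other secondary endpoints are hit harder.** The same term is missing there, but the documents give no figure from which to size it.
- **That a trial conclusion is at risk.** The study is for estimation, with no success criterion, and Protocol 15.10.2 requires no multiplicity adjustment.

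The missing entry in SAP 9.6 is a separate documentation gap. It needs closing whatever ρ turns out to be, but it is not evidence that the interval is too narrow.

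**What to change.** 1. In SAP 8.2, keep the MMRM point estimate. Before forming the interval, add (estimated baseline slope at the visit)² × s²(baseline)/N to the LS-mean variance, for each group and for the combined estimate, with N the number of subjects over whom mean baseline is taken. Equivalently, put Baseline in the response vector with a mean common to both groups and report the Week 24 minus Baseline contrast.
2. State the baseline value at which LS means are evaluated.
3. In SAP 8.3, do the same for Hgb at Week 48, the other MMRM endpoints and the ANCOVA analyses.
4. Show the unadjusted interval of Protocol 15.7.1 as a supporting result only.
5. List the change of primary CI method in SAP 9.6.

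The cost is SAP wording and a few lines of code; no new data are needed. The only downside is slightly wider reported intervals. At the planning SD with complete data, the combined half-width returns to 0.149 g/dL.

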7.5.1. Scheduled Dose Adjustment During the Dose Titration Period

Scheduled study drug titration will occur in Week 12 and will be based upon the Hgb increase relative to Baseline and an Hgb threshold. The Baseline assessment value is the last non-missing value prior to the subject's first dose of study medication. If the Week 12 assessment is missing, the Hgb increase from Baseline will be assessed based on the first non-missing value after Week 12.

Those subjects with an Hgb increase of ≥ 0.5 g/dL from Baseline and an Hgb ≥ 10 g/dL will maintain the same dose as determined at Randomization; subjects with an Hgb increase < 0.5 g/dL from Baseline or an Hgb < 10 g/dL will have their dose of KRX-0502 increased as shown in [Table 3](#).

Due to the random variability of Hgb values, if a Hgb level at Visit 6 (Week 12) appears not plausible (as defined as more than 1 g/dL difference from the most recent Hgb value obtained in the prior 6 weeks), the Investigator may choose to repeat it. In that case, the Hgb from the repeat laboratory draw will determine the dose titration.

For subjects with a scheduled dose titration, the dose change should begin the day after notification.

Table 3: Scheduled Study Drug Titration After Visit 6 (Week 12)

Study Drug Titration at Week 12	
Group 1 (starting dose: 1 tablet TID with meals)	
Hgb increase ≥ 0.5 g/dL from Baseline and an Hgb ≥ 10 g/dL	No change
Hgb increase <0.5 g/dL from Baseline or an Hgb <10 g/dL	2 tablets TID (total of 6 tablets/day) with meals
Group 2 (starting dose: 2 tablets BID with meals ^a)	
Hgb increase ≥ 0.5 g/dL from Baseline and an Hgb ≥ 10 g/dL	No change
Hgb increase <0.5 g/dL from Baseline or an Hgb <10 g/dL	3 tablets BID (total of 6 tablets/day) with meals ^a

BID=twice daily; Hgb=hemoglobin; TID=3 times daily. The baseline assessment value is the last non-missing value prior to the subject's first dose of study medication.

^a Dose to be taken with the largest 2 daily meals

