## 9.6. Summary of Changes from Protocol-Specified Analyses

- The protocol states that “All subjects who are randomized and take at least 1 dose of study medication will be included in the Safety Analysis Set.” However, the Safety Analysis Set is being defined as the set of all subjects who receive at least one dose of study medication, to allow for the highly unlikely possibility that some subject (s) may receive a dose of medication prior to being randomized.
- The protocol did not discuss the potential for an ad hoc analysis. The analysis is acknowledged in this SAP and more details will be added to an amended SAP if an analysis is performed.
- The protocol did not discuss the modified Per Protocol Analysis Set. This analysis set is described in section 6.3.6 and is used for the 24-Week analysis snapshot only.
- The SAP describes analyses for the following secondary efficacy endpoints which were not included in the protocol:
  - Time from randomization to first hemoglobin increase of  $\geq$  0.5 g/dL from Baseline.
  - Change from the baseline value for each of the following:
    - eGFR
    - serum bicarbonate
    - intact parathyroid hormone
    - C-terminal fibroblast growth factor 23
    - intact fibroblast growth factor
  - Inclusion of box and scatter plots over time of the observed value and the change from Baseline for each of the iron parameter efficacy variables, TSAT and ferritin to explore the question of their stability over time on treatment.
- The protocol specified analyses of vital signs is not included in the SAP, since no related safety concerns are anticipated.

- The protocol states that all efficacy analyses will be performed based on both the FAS and the PP/mPP analysis sets, however only the PP/mPP analyses sets will be considered. Subjects are excluded from the PP/mPP analysis sets due to confounders of efficacy and thus the FAS is not appropriate for efficacy analyses. The FAS will be used for the efficacy analysis for the 'Permitted' ESA Rescue Therapy subgroup.
- The protocol did not include the baseline by visit interaction term in the efficacy model. This interaction term is included in the SAP and will be included in the model.
- Missing endpoint observations will not be imputed using a multiple imputation (MI) linear regression approach for use in an additional sensitivity analysis as specified in the protocol sections 15.7.2 and 15.10.3.

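### SAP 8.2 and 8.3 allow valid Hgb values to be dropped, or data transformed, after the residuals are seen, with no criterion and no guaranteed all-data model result

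*SAP*

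**What the plan says.** SAP 8.2 fits an MMRM to the change from Baseline in Hgb and then checks it: "to detect potential outliers a normal probability plot of residuals and a plot of the residuals versus the fitted values will be used". The next step is: "If necessary, transformations and/or dropping of outliers to obtain data that meet the model assumptions will be implemented". SAP 8.3 attaches the same rule to the ANCOVA for subjects who complete Week 24 or Week 48: "If necessary, transformations and/or dropping of outliers to obtain data that meet these assumptions will be implemented".

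The rule reaches further than Hgb. SAP 8.3 asks for the same kind of statistics for TSAT, ferritin, phosphate, eGFR and bicarbonate, and for the same kind of ANCOVA for iPTH and the two FGF23 assays.

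The primary model output in SAP 8.2 is the "least squares mean (LSM) change from Baseline Hgb obtained using the MMRM described above and the corresponding 95% confidence interval", shown with descriptive statistics by visit. Protocol 15.7.1 says only "Ninety-five percent CIs will be constructed for change from Baseline at Week 24" (and at Week 48), with no imputation. Protocol 15.7.2 and 15.10.3 contain no outlier rule, and SAP 9.6 does not list one among its changes from the protocol.

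**The concern.** The decision to drop or transform is taken after the outcome residuals are seen, in an open-label trial, and the stated aim is to make the data fit the model. Nothing says how far out a value must lie, who decides, or that the untouched fit will also be shown. A reduced or transformed fit could therefore be the only model estimate reported.

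Three things follow:

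- Removing extreme values shrinks the residual variance, so the interval can be too narrow. If the tails are unequal, the mean also shifts.
- SAP 8.2 and 6.6.1 rest on data missing at random. A value deleted because of its own residual is missing because of its own size, so the rule creates missingness that the model assumes away.
- A non-linear transformation no longer estimates a mean change in g/dL, which is the primary endpoint.

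The cross-checks are thin. SAP 9.6 drops the protocol's FAS analyses ("however only the PP/mPP analyses sets will be considered"), apart from the permitted-ESA subgroup, and also drops its multiple-imputation analysis. The remaining Hgb cross-check, the completer ANCOVA, carries the same outlier rule.

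**Working it through.** **1. The plan's own figure.** Protocol 15.2 and SAP 4.3.1 give SD 0.9 g/dL, 140 evaluable subjects (70 per group) and a half-width of 0.149 g/dL.

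- All subjects: 1.96 × 0.9 / √140 = 0.149. This reproduces.
- Per group: 1.96 × 0.9 / √70 = 0.211 (0.215 using t).

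**2. What trimming does to the width in normal data.** The width ratio is (SD of the truncated normal) / √(1 − fraction dropped).

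| Cut-off | Fraction dropped | SD ratio | Width ratio |
|---|---|---|---|
| 2 SD | 0.0455 | 0.880 | 0.880/√0.9545 = 0.90 |
| 2.5 SD | 0.0124 | 0.955 | 0.955/√0.9876 = 0.96 |
| 3 SD | 0.0027 | 0.987 | 0.987/√0.9973 = 0.99 |

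**3. Coverage of a nominal 95% one-sample t interval, by simulation (20,000 runs per cell).** The SAP gives no cut-off, so 2, 2.5 and 3 SD are assumed. Gated means that values are dropped only if a Shapiro-Wilk test gives p < 0.05, as a stand-in for the visual check. Ungated means always dropped.

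| Case | n = 70 (2 / 2.5 / 3 SD) | n = 140 (2 / 2.5 / 3 SD) |
|---|---|---|
| Normal, gated | 94.6 / 95.0 / 95.1% | 94.4 / 94.8 / 95.0% |
| Normal, ungated | 89.3 / 92.8 / 94.2% | 89.4 / 92.8 / 94.2% |
| 5% of subjects average 2.5 g/dL higher, gated | 88.3 / 91.2 / 92.9% | 81.3 / 87.1 / 91.2% |
| – bias in that case (g/dL) | -0.052 / -0.040 / -0.025 | -0.066 / -0.052 / -0.032 |
| 5% of subjects average 1.5 g/dL higher, gated | 93.7 / 94.4 / 94.7% | 92.7 / 93.9 / 94.4% |

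A low-responder tail (5%, 2.5 g/dL lower) was also run gated. Subjects with Hgb below 8.0 g/dL were removed first, as a proxy for the ESA-rescue and per-protocol exclusions (Protocol 9.2.2, SAP 6.3.5). Coverage was 93–95% and bias at most +0.011 g/dL. Keeping all data gave about 95%.

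**4. Other shapes, ungated (40,000 runs, n = 70, cut-offs 2 / 2.5 / 3 SD).** With a t distribution on 5 df, coverage was 90.9 / 93.0 / 93.8%. With a right-skewed gamma (shape 4) it was 73.0 / 85.5 / 90.6%, with bias -0.11 / -0.06 / -0.03 g/dL.

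**5. Repeated-visit model.** Two groups of 70 were simulated at seven visits to Week 24 with the fixed effects in SAP 8.2. Covariance was unstructured, the within-subject correlation was 0.5 or 0.8, and there were 2,000 runs per cell. A fixed 137 df replaced Kenward-Roger.

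- High tail rising to +2.5 g/dL at Week 24, gated: coverage 89–94% by group and 85–94% combined, with bias -0.012 to -0.052 g/dL.
- Normal data, ungated at 2 SD: 90–91% by group.
- All data: about 95%.

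The all-data half-width in the high-tail simulation was 0.248 g/dL per group, wider than the planned 0.215 because the tail raises the SD. The bias is 0.012/0.248 = 5% to 0.052/0.248 = 21% of it.

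**6. Hand check.** Dropping 3 of 70 values lying 2.5 to 3 SD below the mean raises it by 3 × 2.5 × 0.9/67 = 0.10 to 3 × 3 × 0.9/67 = 0.12 g/dL. That is about half of the planned per-group half-width.

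**The case against.** The strongest reply is about size. Under the only distributional input in the documents (SD 0.9) and a conditional reading of the rule, coverage stays at 94–95%. The clear harm needs an assumed tail of 5% of subjects averaging 2.5 g/dL above the rest, which no section supports. At 1.5 g/dL it nearly vanishes. A 2 SD cut would drop about 6 of 140 perfectly normal values, a harsh reading of an outlier. The worst repeated-visit bias, 0.05 g/dL, is a tenth of the 0.5 g/dL change used at Week 12. All of this stands. It limits the size of the problem but supplies no criterion.

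The second reply is transparency. SAP 8.2 gives descriptive statistics, SAP 8.3 box plots, and SAP 9.4 laboratory summaries for the Safety Analysis Set and by-subject listings. A reader could probably detect trimming and compute a crude interval. That also stands, but none of these is the adjusted model estimate with its interval. The separate table shells (SAP 11.5) might show both fits; they were not available.

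Third, SAP Section 2 places analysis decisions before database lock. This fixes timing only. The plots need outcome data in an open-label trial, and SAP 5 plans a Week 24 snapshot for publication.

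Fourth, the plausibility limit in Protocol 7.5.1 ("as defined as more than 1 g/dL difference from the most recent Hgb value obtained in the prior 6 weeks") governs an optional repeat draw for a dosing decision, not exclusion from analysis. Agreed. It shows only that a numeric definition was feasible.

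Finally, both groups are active, Hgb is a central-laboratory value, and the aim is estimation. This reduces the room for bias but leaves the interval exposed. The transformation part was not simulated; it rests on the change of estimand alone.

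**Conclusion.** The concern holds. SAP 8.2 and 8.3 contain an active rule for changing the analysed data after the residuals are seen. They give no criterion, no limit to documented errors and no guaranteed all-data fit, and no other section supplies these. The consequence ranges from none (near-normal data, cautious use) to material: 81–93% one-sample coverage, or 85–94% in the repeated-visit model, with bias up to about 0.05–0.07 g/dL under the assumed 2.5 g/dL high tail. Those figures rest on assumed cut-offs, an assumed tail and a formal test standing in for a visual judgement, so confidence in the size is moderate. The defect in the text does not depend on them. It should be corrected, but it does not invalidate the design.

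**What to change.** Replace the sentences in SAP 8.2 and 8.3 with wording such as:

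> The primary and secondary Hgb models keep all valid central-laboratory values on the g/dL scale. Only documented laboratory or data errors are removed, before database lock. Any outlier-excluded, robust or transformed Hgb fit is a sensitivity analysis reported beside the all-data result. For other endpoints, no valid value is dropped on its residual. If a transformation is used for a skewed marker (ferritin, iPTH, FGF23), it is named before lock and the untransformed all-data result is reported alongside.

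The clause on other endpoints is needed because they inherit the rule through SAP 8.3; their size of effect was not computed. For the snapshot, documented errors should be settled before that data cut as well.

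The cost is SAP wording only, with no new data. The interval may be slightly wider than after trimming, and one extra model output is needed where a transformation is used.
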